## APPENDIX 2. PROFESSIONAL RESVINET CLINICAL SCORING SYSTEM

Assessment Period	Item	0 points	1 point	2 points	3 points
Over the last 24 hours	1 Feeding intolerance	None	Mild Decreased appetite and/or had isolated vomiting with coughing.	Partial Frequently vomits with coughing. rejected feeds but able to tolerate fluids sufficiently to ensure hydration.	Total Intolerance or absolute rejection of feeds, unable to maintain adequate hydration orally. Required nasogastric and/or intravenous fluids
Over the last 24 hours	2 Medical intervention	None	Basic Nasal secretion aspiration performed, trial of nebulized bronchodilators, antipyretics.	Intermediate Oxygen therapy required. Supplementary testing needed (eg, chest X-rays, blood gases). Ongoing nebulized bronchodilators.	High Required respiratory support with positive pressure (either non-invasive in continuous positive airway pressure (CPAP), bilevel positive airway pressure (BiPAP) or high- flow O 2 ; or invasive through endotracheal tube).
As examined	3 Respiratory difficulty	None	Mild Not feeling as usual but does not look severely ill. Respiratory wheezing audible only with stethoscope, good air entry. If modified Wood Downes, Wang score, or any other respiratory distress score is applied, it indicates mild severity.	Moderate Makes some extra-respiratory effort (intercostal and/or tracheosternal retraction). Expiratory wheezing is audible even without stethoscope, and air entry may be decreased in localized areas with stethoscope. If modified Wood Downes, Wang score, or any other respiratory distress score is applied, it indicates moderate severity.	Severe Respiratory effort is obvious. Inspiratory and expiratory wheezing and/or clearly decreased air entry with stethoscope. If modified Wood Downes, Wang score, or any other respiratory distress score is applied, it indicates high severity.

#### To be completed by site Investigator or designee

Assessment Period	Item	0 points	1 point	2 points	3 points
Over the last 24 hours	4 Respiratory frequency	Normal <2 m: 40-50 bpm 2-6 m: 35-45 bpm 6-12 m: 30-40 bpm 12-24 m: 25-35 bpm 24-36 m: 20-30 bpm	Mild or occasional tachypnea Episodes of tachypnea are present but well tolerated, limited in time, and self- resolving or responding to aspiration of secretions or nebulization.	Prolonged or recurrent tachypnea Tachypnea persisted or recurred despite aspiration of secretions and/or nebulization with bronchodilators.	Severe alteration Severe and sustained tachypnea. Breathing that is very superficial and rapid. Normal/low rate breath with obvious increased respiratory effort and/or mental status changes. Rates of severe tachypnea: <2 m: >70 bpm 2-6 m: >60 bpm 6-12 m: >55 bpm 12-24 m: >50 bpm 24-36 m: >40 bpm
Over the last 24 hours	5 Apnea	No			Yes At least one episode of medically documented apnea or one which is strongly suggested by history.
As examined	6 General Condition	Normal	Mild Not feeling as usual, child was mildly uncomfortable but does not appear to be severely ill. Parents are not alarmed. Could wait in the waiting room or even stay at home.	Moderate Patient looks ill and required medical examination and eventually further complementary exams and/ or therapy. Parents are concerned. Cannot wait in the waiting room.	Severe Agitated, apathetic, lethargic. Severity is self-evident. Parents are very concerned. Immediate medical evaluation and/or intervention were required.
Over the last 24 hours	7 Fever	No	Yes, Mild fever, central temp <38.5°C	Yes, Moderate fever, central temp >38.5°C	

## To be completed by site Investigator or designee

Source of information other than assessment period: Table 1 in Justicia-Grande et al, PLOS One, 2016 (doi:10.1371/journal.pone.0157665.t001)

Abbreviations: m = months

## APPENDIX 3. PARENT/GUARDIAN RESVINET CLINICAL SCORING SYSTEM AND PALATABILITY QUESTION

Assessment Period	Item	0 points	1 point	2 points	3 points
Over the last 24 hours	1 Feeding intolerance	None	Mild Decreased appetite (the child ate less than usual) and/or had isolated vomiting with coughing.	Partial Frequently vomits with coughing, but the child does not vomit with every feed. Feeding exhausts the child.	Total The child is unable to feed him/herself. The use of a nasogastric tube or parenteral nutrition was required.
Over the last 24 hours	2 Medical intervention	None	Basic The child's respiratory secretions needed to be removed, he or she was examined by a doctor or received occasional nebulized medication. Medication to treat fever was given.	Intermediate The child required oxygen therapy, underwent a chest X-ray, or a blood sample was taken. Treatment with nebulized medication was given regularly.	High The child required respiratory support with a machine. Respiratory support was given through a special mask applied to the nose or mouth or resting on the child's face, or through an endotracheal tube.
When the diary was completed	3 Respiratory difficulty	None	Mild The child was not breathing normally, but he/she does not seem to have any difficulty when breathing in.	Moderate The child finds breathing is an effort. Respiratory noises can be heard just by pressing your ear close to his or her chest (without a stethoscope)	Severe Respiratory effort is obvious. The child makes significant movements of his/her chest, the chest even collapses with every movement, and muscles of neck and belly were used. A lot of respiratory noise is heard without pressing the ear close to the child's chest.

#### To be completed by parent/caregiver

Assessment Period	Item	0 points	1 point	2 points	3 points
Over the last 24 hours	4 Respiratory frequency	Normal	Mild or occasional tachypnea The child was breathing more rapidly but it was well tolerated, or the breathing became normal after removing secretions from the child's airways or administering nebulized medication.	Prolonged or recurrent tachypnea The child was breathing more rapidly and persistently, even after receiving nebulized medication or removing secretions from the child's airway.	Severe alteration The child breathed quickly and superficially, or really deeply. The child was agitated or drowsy. The child was severely short of breath.
Over the last 24 hours	5 Apnea	No			Yes The child stopped breathing. It may have been necessary to stimulate him/her to start normal breathing.
When the diary was completed	6 General Condition	Normal	Mild The child is not feeling as usual, but there does not seem to be anything to worry about.	Moderate Child looked ill, and medical examination was required, but it did not feel like a life- threatening situation.	Severe Child was agitated, apathetic, and/or lethargic. He/she required urgent medical attention. There was no need to be a doctor to see that the condition of the child is worrying.
Over the last 24 hours	7 Fever	No	Yes, Mild Rectal or tympanic temperature <38.5°C, or axillar temperature <38°C	Yes, Moderate Rectal or tympanic temperature >38.5°C, or axillar temperature >38°C	

### To be completed by parent/caregiver

Source of information other than assessment period: Table 2 in Justicia-Grande et al, PLOS One, 2016 (doi:10.1371/journal.pone.0157665.t001) m = months

# **Palatability Question**

Did the child take the medicine? (yes/no)

Select all that apply:

- □ Successfully swallowed the medicine without vomiting within 2 minutes of swallowing;
- $\Box$  Took the study medication easily;

- $\hfill\square$  The facial expression suggested that he/she did not like the taste;
- $\Box$  Cried after tasting it;
- $\Box$  Would not open mouth or turned head away to avoid it;
- $\Box$  Spit out or coughed it out;
- □ Gagged or vomited (within 2 minutes of swallowing medicine).

3

### LIST OF ABBREVIATIONS

AE	adverse event
ATC	Anatomical Therapeutic Chemical
AUC	area under the curve
ANCOVA	analysis of covariance
BMI	body mass index
CaGI-S	Caregiver Global Impression of Severity
CaGI-C	Caregiver Global Impression of Change
CI	confidence intervals
DAIDS	Division of AIDS
ECG	electrocardiogram
eCOA	electronic clinical outcome assessment
eCRF	electronic case report form
EOS	end-of-study
EOT	end-of-treatment
FDA	Food and Drug Administration
GFR	Glomerular Filtration Rate
ICF	informed consent form
ICH	International Council for Harmonisation
ICU	intensive care unit
LLN	lower limit of normal
LLOQ	lower limit of quantification
LOD	limit of detection
MAARI	Medically Attended Acute Respiratory Infection
MedDRA	Medical Dictionary for Regulatory Affairs
MMRM	Mixed-effect model for repeated measures
NCI-CTCAE	National Cancer Institute Common Terminology Criteria for Adverse Events
РК	pharmacokinetic(s)
PKPD	Pharmacokinetic-Pharmacodynamic
PT	preferred term
QD	Once Daily
RESOLVE-P	Respiratory Observable Reported Outcome - Pediatric
RSV	respiratory syncytial virus
RT-qPCR	quantitative reverse transcription polymerase chain reaction
SAE	serious adverse event
SAF	Safety (for the analysis population)

SAP	statistical analysis plan
SoA	Schedule of Assessments
SOC	system organ class
SSC	Study Steering Committee
TD	Target Detected
TEAE	treatment-emergent adverse event
TFLs	tables, figures, and listings
TND	target not detected
ULN	upper limit of normal
WHO	World Health Organization

# 1. INTRODUCTION

EDP-938 (also known as EPC-3938, EPS-3938, and EP-023938) is a novel, orally administered, nonfusion replication inhibitor of respiratory syncytial virus (RSV) that is being developed as a potential treatment for RSV infection. This Phase 2 study, EDP 938-201, is a randomized double-blind, placebocontrolled, 2-part study to evaluate the safety, tolerability, pharmacokinetics (PK), clinical outcome, and antiviral activity of orally administered EDP-938 regimens in hospitalized or non-hospitalized infants and children aged 28 days to 36 months infected with RSV.

The preparation of this Statistical Analysis Plan (SAP) is based on the International Conference on Harmonization (ICH) E9 guidelines [1] and study protocol Version 18.0 dated 09 July 2024. The SAP outlines the statistical analyses of the efficacy and safety data to support the clinical study report (CSR) and will be finalized prior to the database lock. Any changes to the SAP after finalization will be documented in the CSR. The table of contents and shells for the tables, figures, and listings (TFLs) will be produced in a separate document.

# 2. STUDY DESIGN

This is a Phase 2, dose-ranging, randomized, double-blind, placebo-controlled, 2-part study to evaluate the safety, tolerability, PK, clinical outcome, and antiviral activity of orally administered EDP-938 regimens in infants and children aged 28 days to 36 months with RSV-associated respiratory tract infection, who are hospitalized or non-hospitalized.

Each part of the study has 3 periods: Screening, Treatment, and Follow-up. For each subject, the duration of study will be approximately 29 days (Table 1). Study site visits and assessments are detailed in the Schedule of Assessments (SoA; Appendix 7.1).

The end of the study will be defined as the last visit of the last subject enrolled.

#### Table 1

Study Period	Duration
Screening (Day -1 to Day 1)	Up to 24 hours (note: some assessments done as part of standard of care can be used as screening assessments if they are done within 72 hours)
Treatment (Day 1 to Day 5)	5 days
Follow-up (Day 6 to Day 28)	23 days
Approximate total duration of participation	29 days maximum

### Figure 1: Study Design

QD = once daily; SSC = study steering committee; TBD = to be determined. The SSC will review data from each cohort and will determine dose selection and cohort progression in Part 1 and Part 2.

\*SSC will review available blinded data when at least 9 subjects have been randomized in Cohort 1 for each age group.

Page 10 of 55 CONFIDENTIAL \*\* SSC will review available blinded data when at least 6 subjects have been randomized in Cohort 2 for each age group.

#### 2.2 Treatment Assignment/Randomization and Blinding

The study will be double-blinded, meaning that the subjects and their caregivers, investigators, and site staff will be blinded to treatment assignment until the completion of the study.

Subjects will be randomized to a treatment group using an Interactive Web Response System.

Subjects will be randomized to the initial EDP-938 or placebo treatment group as shown below:

Part 1, Cohort 1, Age Group 1 and 2 (randomized 2:1)

- of EDP-938 orally QD for 5 days (8 subjects);
- placebo orally QD for 5 days (4 subjects).

The dose for Part 1 Cohort 2 for each age group will be determined based on review of Part 1 Cohort 1

data.

#### Part 2, Age Group 1 and 2 (randomized 4:1)

EDP-938 orally QD for 5 days: dose to be determined

- Oral EDP-938 QD for 5 days: dose to be determined (16 subjects);
- Oral placebo QD for 5 days: dose to be determined (4 subjects).

# **3. OBJECTIVES AND ENDPOINTS**

#### 3.1 Objectives

The primary efficacy objective is to evaluate the antiviral activity of EDP-938 in the pooled population (subjects from Part 1 and Part 2 together).

#### 3.1.1 Part 1: Primary and Secondary Objectives

#### **Primary Objectives**

- To evaluate the PK of EDP-938
- To assess the safety and tolerability of EDP-938

#### **Secondary Objective**

• To evaluate the antiviral activity of EDP-938

#### 3.1.2 Part 2 and Pooled Population: Primary and Secondary Objectives

#### **Primary Objective**

• To evaluate the antiviral activity of EDP-938

#### **Secondary Objectives**

- To assess the safety and tolerability of EDP-938
- To evaluate the PK of EDP-938
- To evaluate additional antiviral activity measures of EDP-938
- To evaluate clinical outcomes of EDP-938

# 3.2 Endpoints

The primary efficacy endpoint is the daily change in RSV shedding in nasal swab samples determined using RT-qPCR from Baseline through the treatment phase in the pooled population (subjects from Part 1 and Part 2 together).

# 3.2.1 Part 1: Primary and Secondary Endpoints

# **Primary Endpoints**

- PK parameters of EDP-938 including area under the curve (AUC) and predose concentrations
- Safety and tolerability of EDP-938 compared to placebo as assessed by, but not limited to, adverse events (AEs), vital signs, and clinical laboratory results

# **Secondary Endpoints**

- AUC for RSV RNA viral load measured in nasal swab samples by quantitative reverse transcription polymerase chain reaction (RT-qPCR)
- Daily change in RSV shedding in nasal swab samples determined using RT-qPCR from Baseline through the treatment phase
- Proportion of subjects with RSV RNA viral load below the limit of detection (LOD) in subjects receiving EDP-938 compared to placebo
- Time to RSV RNA viral load being undetectable

# 3.2.2 Part 2 and Pooled Population: Primary and Secondary Endpoints

# **Primary Endpoint**

Daily change in RSV shedding in nasal swab samples determined using RT-qPCR from Baseline through the treatment phase.

# Secondary Endpoints

• Safety and tolerability of EDP-938 compared to placebo as assessed by, but not limited to, AEs, vital signs, and clinical laboratory results;

- AUC for RSV RNA viral load measured in nasal swab samples by RT-qPCR;
- Proportion of subjects with RSV RNA viral load below the LOD in subjects receiving EDP-938 compared to placebo;
- Time to RSV RNA viral load being undetectable;
- PK parameters of EDP-938 including AUC and predose concentrations;
- Time to discharge for hospitalized subjects;
- Time to use of oxygen for hospitalized subjects who are not receiving oxygen at the time they receive the first dose of study drug;
- Proportion of hospitalized subjects requiring oxygen supplementation or have an increased oxygen requirement;
- Time to mechanical ventilation for hospitalized subjects;
- Proportion of hospitalized subjects requiring mechanical ventilation;
- Deaths among hospitalized subjects;
- Time to hospitalization for initial outpatients who are subsequently hospitalized;
- Proportion of outpatients who are subsequently hospitalized or died;
- Time to resolution of symptoms for outpatients who are not hospitalized.

# 4. STATISTICAL CONSIDERATIONS

# 4.1 General Considerations

All statistical procedures will be completed using SAS version 9.4 or higher.

Continuous variables will be summarized using descriptive statistics (i.e., n, mean, standard deviation (SD), median, 25th percentile, 75th percentile, minimum and maximum values). The mean, median and the percentiles will be rounded to one decimal place beyond the precision of the values being summarized; the SD will be rounded to 2 additional decimal places beyond this precision and the minimum and maximum values will be displayed in the same precision. If n=0, then display n and leave all other statistics blank. If n=1, display "N/A" for SD.

Categorical variables will be summarized using frequency counts and percentages. The denominator for the percentages will be the number of subjects in the appropriate age group and treatment group within the analysis set of interest, unless otherwise specified. The denominator will be displayed when needed and the percentage will be rounded to one decimal place. If the frequency is 0, the percentage will not be displayed. A row denoted "Missing" will be included in count tabulations where specified on the shells to account for dropouts and missing values where applicable.

All subject data, including those derived, will be presented in individual subject data listings. Unless otherwise stated, unscheduled visit results will be included in date/time chronological order, within subject listings. All listings will be sorted by study part, treatment group, subject number, date/time and visit. The treatment group (randomized) as well as subject's sex, race, age and age group will be stated on each listing. Unless otherwise stated, data listings will be based on all subjects randomized.

Baseline, unless otherwise specified, will be defined as the last non-missing assessment collected before or on the date of first dose of study drug. For analyses of nasal swab data and analyses of RSV-related signs and symptoms, if assessments before the first dose of study drug are not available, a post treatment assessment collected no more than 60 minutes after the first dose of study drug will be used as the baseline value.

Efficacy summary tables and figures will be presented by randomized treatment group and age group for Part 1 and Part 2 separately and will be labelled as follows. Additionally, efficacy summary tables and figures for efficacy endpoints for the pooled population will be summarized using pooled data (subjects from Parts 1 and 2) as appropriate. Other summaries including disposition, analysis populations, demographics, and baseline data will be displayed by treatment group, age group for Parts 1 and 2 separately. Parts 1 and 2 will also be pooled for these summaries.

Age Group:

- " $\geq 6$  to  $\leq 36$  months"
  - $\circ$  " $\geq 6$  to <12 months"
  - $\circ$  " $\geq 12$  to  $\leq 36$  months"
- " $\geq 28$  days to <6 months"
  - $\circ$  " $\geq$ 28 days to <3 months"

 $\circ$  " $\geq$ 3 to <6 months"

Treatment:

- "EDP-938"
- "Placebo"

Study Part:

- "Part 1"
- "Part 2"
- "Parts 1 and 2"

Safety summary tables and figures will be summarized separately for Part 1 and Part 2 as well as pooled Parts 1 and 2 data by the actual treatment group. In addition, pooled Parts 1 and 2 data will be summarized by age group.

For the reporting of this study both CDISC SDTM (SDTM Implementation Guide version 3.3 or later) and ADaM (ADaM Implementation Guide version 1.1 or later) standards will be applied. A subject will be considered to have completed the study after his/her attendance at the last planned study visit (Day 28  $\pm$  4 day), or the last unscheduled visit (if any occur), as applicable. For each subject his or her study completion status (Yes/No) is recorded on the End of Study CRF.

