# 11. STATISTICAL CONSIDERATIONS

## 11.1. Sample Size Considerations

## 11.2. General Considerations

Statistical analysis of this study will be the responsibility of Enanta Pharmaceuticals, Inc. or its designee. Details of the statistical analysis methods will be described in the statistical analysis plan (SAP) document. Statistical methods are primarily descriptive in nature and will be used to guide decisions as to the clinical relevance of findings. No formal statistical analysis is planned. Parts 1 and 2 will be summarized separately unless stated otherwise.

Unless otherwise specified, baseline will be defined as the last non-missing measurement before the first dose of study drug. For analyses of nasal swab data and analyses of RSV-related signs and symptoms, if assessments before the first dose of study drug are not available, a post-treatment assessment collected no more than 60 minutes after the first dose of study drug will be used as the baseline value. Any change to the data analysis methods described in the protocol will require an amendment if it changes a principal feature of the protocol. Any other change to the data analysis methods described in the protocol, and the justification for making the change, will be described in the clinical study report or SAP. Changes may only be made in the SAP before unblinding.

The presence of a coinfection will be taken into consideration when analyzing the results of the study.

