\* The ReSVinet assessments will be completed predose QD each day, by subjects' parent(s)/guardian(s), through Day 14 and at approximately the same time each day ±2 hours. The palatability question will be completed as soon as possible after each dose of study drug is administered. The RESOLVE-P assessments will be completed twice daily (AM and PM), approximately every 12 hours for 14 days. The D1 assessment must be completed pre-dose. Only one D1 assessment is expected if completed in the afternoon.

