# 4.13 Efficacy Analyses

All efficacy analyses will be based on the Efficacy Population. Selected efficacy endpoints will also be based on the mITT-3 and mITT-5 populations. Part 1 data and Part 2 data will be summarized separately using descriptive statistics. In addition, all secondary efficacy endpoints in Part 2 as well as all exploratory endpoints will be summarized based on pooled data from both Parts 1 and 2. Inferential statistical analysis will be performed to these pooled analyses, as appropriate.

# 4.13.1 Primary Efficacy Analysis Part 1

Not applicable because the primary endpoint for this part of the study is the PK analysis (please refer to *Section 4.15.1*)

# 4.13.2 Secondary Efficacy Analysis Part 1

The following secondary endpoints will be analyzed descriptively using the Efficacy, mITT-3, mITT-5 Populations.

• AUC for RSV RNA viral load measured in nasal swab samples by quantitative reverse transcription polymerase chain reaction (RT-qPCR)

RSV RNA viral load will be measured in nasal swab samples by RT-qPCR on Days 1, 3, 5, 9 and 14. Viral load values reported as TD (Target Detected, but below LLOQ) will be set to the average of LOD (limit of detection) and LLOQ (lower limit of quantification). Viral load values reported as TND (Target Not Detected, below LOD) will be set to zero. Viral load data will be transformed using a log10 scale before analyses. In case of zero value, the log transformed value will be also set as zero. For the RT-qPCR assay used for detection and quantification of RSV A and RSV B, the LLOQ is 1000 copies/mL for RSV A and 250 copies/mL for RSV B; the LOD is 620 copies/mL for RSV A and 80 copies/mL for RSV B.

The RSV type of each subject will be decided at baseline based on the RT-qPCR test. The baseline RSV viral load result is from the nasopharyngeal swab sample taken after randomization and prior to first dose on Day 1. After the imputation of TD, TND, and log10 transformation, if the baseline RSV A viral load is greater than RSV B viral load, the baseline

RSV type is classified as RSV A. Further, if the baseline RSV B viral load is greater than RSV A viral load, the baseline RSV type is classified as RSV B.

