Visit	Screening	V1	V2	V3	V4	V5	PT1	PT2	PT3 	and V4 assessments will be done at home. (X) is for V2 and V4 assessments for hospitalized subjects.
Dav	Day-1 to Day 1	1	2	$\frac{3}{(\pm 1)^4}$	4	5 (±1) EOT 	9 (±1)	14 (±2)	28 (±4) EOS 	Notes  : Protocol Section
Physical examination	X			X		х	X	X		Full PE at Screening. Subsequent PEs done at discretion of Investigator will be targeted to new signs and symptoms, including specific assessments of changes from previous status. Section 8.6
ECG	х					Х				12-lead ECG strongly preferred but where not possible, 6-lead ECG may be performed. If blood sampling and/or a nasal swab are scheduled for the same timepoint as ECG recording, those assessments should be done after the ECG. Section 8.5
Procedures					•					Residual samples from blood and/or nasal swab volume may be used for exploratory biomarker analyses. Section 8.14
Nasal swab		Х		Х		X	Х	X		Swab samples should be taken at approx. same time before study drug administration. One swab will be collected at each visit. Section 8.12
Blood sampling for clinical laboratory tests	Х	X*		X		х				Clinical laboratory tests include biochemistry, hematology, and cardiac biomarkers. All clinical laboratory tests that will be evaluated in the study are specified in Table 3. Evaluations will be conducted by local laboratories. *For subjects who have screening and randomization separated by more than 24 hours, blood sampling for clinical laboratory tests should be done predose on Day 1 for baseline values. This blood sampling does not need to be done for subjects who have randomization within 24 hours after screening because the screening clinical laboratory test results will be used as the baseline values. Section 8.11
Urinalysis	Х					X				Urine will be collected only from subjects who are either toilet trained and able to provide a specimen or are already catheterized or fitted with a urine collection bag, Section 8.11

Study Period	Screening 	Trea	tme	nt			Follow	-Up		For non-hospitalized subjects, V2
Visit	Sanooning	V1	V2	V2	VA	V5	DT1	DT2	DT23	and V4 assessments will be done at home. (X) is for V2 and V4 assessments for hospitalized subjects.
V ISIL	Day_1 to	V I	¥ 2	3	V 4	$\frac{\sqrt{3}}{5(+1)}$	0	112	$\frac{113}{28(+4)}$	
Day	Day 1 Day 1	1	2	$(\pm 1)^4$	4	$EOT^5$	(±1)	(±2)	$EOS^5$	Notes  ; Protocol Section

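### SAP 4.1 sets the general baseline by calendar date rather than by dose time, so read literally it can select a post-dose Day 1 value for RESOLVE-P and for repeat safety measurements

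*SAP*

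**What the plan says.** Protocol 11.2 gives the general rule: "baseline will be defined as the last non-missing measurement before the first dose of study drug". SAP 4.1 gives a different one: the "last non-missing assessment collected before or on the date of first dose of study drug". Both apply unless something else is specified.

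Both documents then make the same exception for nasal swab data and RSV-related signs and symptoms. In the SAP's words, "if assessments before the first dose of study drug are not available", then "a post treatment assessment collected no more than 60 minutes after the first dose of study drug will be used as the baseline value". The protocol's version allows an "assessment collected no more than 60 minutes after the first dose of study drug will be used as the baseline value".

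For viral load, SAP 4.13.2 is more specific: the baseline result comes from the swab "taken after randomization and prior to first dose on Day 1".

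On timing of the caregiver instrument, the footnote to SAP 4.5 states: "The RESOLVE-P assessments will be completed twice daily (AM and PM), approximately every 12 hours for 14 days". The Day 1 entry must precede dosing, and only one entry is expected that day if it is made in the afternoon.

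**The concern.** The SAP replaces a cut-off at the moment of dosing with a cut-off at the end of that calendar day, and then takes the last value. A programmer who follows the sentence as written will pick a post-dose Day 1 record whenever one exists. The rule is not limited to scheduled assessments.

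A post-dose baseline can absorb an early drug effect or an early safety signal. For RESOLVE-P it would alter change from baseline and the baseline term in any repeated-measures model of that score. For laboratory data, SAP 4.14.2 calls a result treatment-emergent high only if the baseline was at or below the upper limit. A high value drawn after the first dose and then taken as baseline could therefore no longer appear as a shift. Vital-sign change from baseline (SAP 4.14.3) would be affected in the same way.

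**Working it through.** No sample-size or power figure is involved. The check sets the rules side by side and applies the SAP rule to each Day 1 assessment.

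**Post-dose time that each rule admits**

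- Protocol 11.2, general rule: 0 minutes.
- Protocol 11.2 and SAP 4.1, exception for swabs and RSV symptoms: up to 60 minutes, only if there is no predose value.
- SAP 4.1, general rule read literally: the rest of the calendar day of first dose, even if a predose value exists.

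The last two cannot both be operative for swabs and symptoms. If any same-day value already qualifies, a 60-minute limit excludes nothing. SAP 4.1 is thus inconsistent within itself as well as with the protocol.

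**The SAP rule applied by assessment**

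1. *Viral load.* SAP 4.13.2 specifies the predose swab. The schedule in SAP 7.1 agrees: "Swab samples should be taken at approx. same time before study drug administration. One swab will be collected at each visit". There is one Day 1 swab, so no later one can displace it. Not affected.
2. *Parent/Guardian and Professional ReSVinet.* One Day 1 assessment each, required predose (Protocol 8.10.2 and Appendix 1). Not affected.
3. *Scheduled vital signs.* Screening values serve as baseline if taken on the same calendar day as Visit 1; otherwise Visit 1 values are taken predose (SAP 7.1). Not affected.
4. *Scheduled laboratory tests.* The screening result, or a predose Day 1 draw if screening and randomization are more than 24 hours apart (Protocol 8.11). Not affected.
5. *Repeat or unscheduled Day 1 vital signs or laboratory tests.* Children are monitored on site for 3 hours after the first dose, and hospitalized children have ongoing monitoring (Protocol 7.1.2). SAP 4.5 assigns Day 1 by nominal visit, which does not separate predose from post-dose. A post-dose repeat, if taken, qualifies under SAP 4.1 and, being last, is selected. Exposed.
6. *RESOLVE-P (subset).* A child first assessed in the morning can have a predose entry and an evening entry. SAP 4.5 maps both to Analysis Visit 1. The first sentence of the SAP rule selects the evening entry; the fallback sentence implies the predose one. Exposed.

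**How late the evening RESOLVE-P entry would be.** Entries are about 12 hours apart and the first precedes dosing. If the first entry is made d hours before the dose, the second falls about 12 − d hours after it, so somewhat less than 12 hours post-dose. A child first assessed in the afternoon has only the predose entry. The literal rule would therefore mix predose and post-dose baselines according to the hour of enrolment.

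**Weight of one child in a safety table.** Planned numbers (SAP 4.2, with the 2:1 and 4:1 ratios):

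- Part 1: 2 age groups × 2 cohorts × 12 = 48, or 32 EDP-938 and 16 placebo.
- Part 2: 2 × 20 = 40, or 32 and 8.
- Pooled: 64 and 24.

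One hidden laboratory shift changes an EDP-938 incidence by 1/32 = 3.1 percentage points within either part, or 1/64 = 1.6 points pooled. How many such children there would be is not derivable.

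**The case against.** The strongest reply is that the SAP's evident intent is predose. Its rule yields wherever something else is specified, and almost every Day 1 baseline is specified or scheduled predose. RESOLVE-P measures RSV signs and symptoms, so the fallback sentence governs it, and that sentence makes sense only if predose values come first. RESOLVE-P is collected in a subset and is not among the listed primary or secondary endpoints. SAP 4.13.5 refers to a section 4.13.7 for the symptom analyses; it is not in the text available to us and may set its own baseline. The schedule lists no post-dose vital signs or safety laboratory tests on Day 1. Treatment-emergent adverse events are defined from the first dose (SAP 4.14.1) and do not use this rule.

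Most of this stands, and it limits the size of the point. It does not remove it. Intent inferred from one sentence does not correct the plain wording of the sentence before it, and the fallback gives no protection to vital signs or laboratory tests, which lie outside its scope.

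A reader might infer that post-dose values generally replace the predose baseline, including in the primary viral-load analysis and its repeated-measures model. The documents do not support that, because SAP 4.13.2 ties the viral-load baseline to the predose swab. Nor is the protocol's predose rule absolute, since it carries the same 60-minute exception.

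**Conclusion.** The SAP's general baseline rule is wrong as written: it departs from Protocol 11.2 and conflicts with its own fallback. The consequence is limited to two places:

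- the Day 1 evening RESOLVE-P entry, which would carry into the baseline summary (SAP 4.8), the change-from-baseline plots (SAP 4.15.2) and the pooled symptom modelling to which SAP 4.13.5 refers;
- repeat or unscheduled post-dose Day 1 vital signs and laboratory values, which would carry into the safety change and shift tables.

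The primary viral-load baseline and the scheduled ReSVinet, vital-sign and laboratory baselines are not affected.

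The RESOLVE-P part assumes that no unseen SAP section defines its baseline separately. The safety part assumes that post-dose repeats occur. The caregiver severity rating (CaGI-S) would also be exposed if it is collected alongside RESOLVE-P; the available text does not give its schedule. Because SAP section 5 is also unavailable, we do not claim that the change from the protocol is unexplained.

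**What to change.** In SAP 4.1:

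1. Define baseline as the last non-missing assessment before the date and time of first dose.
2. Treat a Day 1 record with no clock time as predose only if it was scheduled predose. Do not use untimed, unscheduled Day 1 records as baseline. This matters for RESOLVE-P, which is completed on paper, whereas the electronic diary stamps date and time automatically (Protocol 8.10.2).
3. Keep the 60-minute fallback for swabs and RSV signs and symptoms, only when no predose value exists.

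The cost is a few sentences and a small change to the baseline derivation. No new data are needed: the time of each on-site dose is recorded (Protocol 5.7), and SAP 4.13.2 already uses the date and time of first dose for the viral-load AUC. Protocol 11.2 allows SAP changes only before unblinding, so the edit should be made before then.
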